10.11 Return and Disposal of IMP

All unused IMP will be destroyed at the trial site by the responsible Study Monitor according to SZB SOP. In case of destruction, a destruction form has to be completed with the information about date and location of destruction, sort and amount of IMP.

10.12 Blinding and Emergency Codes

This trial is double-blinded. After randomization, neither the subjects nor the investigator or sponsor will be aware of the treatment allocation.

The procedure for blinding is described in Section 10.8., details of the application and blinding process are described in an IMP Manual. Emergency envelopes for every subject will be provided by the Study Core Unit (SZB).

10.13 Unblinding

Unblinding may be performed by the trial site using Emergency Codes which are provided to the trial site by the SZB as sealed Emergency Envelopes. These envelopes have to be stored at a location known and accessible to all study personnel. All study personnel have to be specifically trained. Integrity of envelopes is controlled by the Study Monitor.

The investigator should adhere to the randomization procedure of the clinical trial and ensure that the code is only broken according to the protocol.

As a matter of principle, unblinding is only performed after the closing of the database for the final analysis.

However, premature unblinding of a subject subject may be necessary in order not to jeopardise his/her safety (ICH-GCP 5.13.4):

- In emergency situations, if it is necessary for the subject subject's safety, i.e. if the further treatment depends on the knowledge of the investigational medicinal product.
- In the event of accidental administration of the investigational medicinal product to a person who is not a clinical trial subject.
- In the event of the death of a subject, if a causal relationship between the treatment with the investigational medicinal product and death is suspected.

- In the event of SAEs/SUSARs, under certain conditions (causal relationship with the investigational medicinal product).

In emergency situations or in the event of accidental administration of the investigational medicinal product, the decision whether unblinding is necessary lies with the investigator. If possible, the sponsor delegated person/Coordinating Investigator should be consulted first. Date and time of unblinding, name of the person who has broken the blind have to be documented on the respective emergency envelope. Any broken emergency envelope has to be filed in the Investigator Site File (ISF).

10.14 Prior and Concomitant Therapy/Medication

Any concomitant therapy and concomitant medication of a subject should be carried out during the clinical trial in consultation with the (principal) investigator. The concomitant medication is documented in the patient file and in the CRF.

10.14.1 Prohibitions

As a rule, a subject should abstain from smoking during the 7 days of treatment with the IMP. In case a subject deviates from this rule, this should be documented in the patient file and in the eCRF.

It will be discussed in the Data Review Meeting together with the Coordinating Investigator and Biometrician whether the subject will be excluded from the analysis or not.

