11.1.4 Concomitant Medication

The following inhibitors and strong inducers of CYP2A6 are prohibited as concomitant medication during the trial:

- Trancylpromine (e.g. Jatrosom®)
- Desipramin (e.g. Norpramin® Pertofrane®)
- Ketoconazole (e.g. Nizoral®, Terzolin®)
- Valproic acid (e.g. Convulex®, Orfiril®)
- Phenobarbital (e.g. Luminal®)
- Pilocarpine (e.g. Salagen®, Spersacarpin®)
- Clotrimazole (e.g. Canesten®)
- Methoxsalen (e.g. Meladinine®)
- Rifampicin (e.g. Eremfat®, Rifa®)

If the above named agents cannot be discontinued for the trial period, patients cannot be included in the study.

If patients already included into the study have to be treated with the above named drugs due to unforeseen circumstances, an individual estimation of the risk has to be performed by the physician in charge. Depending on the duration of the concomitant treatment, the respective patient should to be excluded from the study. This will be decided by the Investigator in consultation with the Sponsor.

The intake of concomitant medication will be documented in the patient's record and in the e-CRF. However, once concomitant medication use is documented, changes (e.g. in dose or added therapies) may not need to be documented unless they contribute to the follow-up of any safety issue (ICH Guideline E19).

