14.2.4 Definition of Populations Included in the Analysis

This clinical trial will be analysed according to the intention-to-treat (ITT) principle. This means that the subjects will be analysed in the treatment arms to which they were randomised, irrespective of the occurrence of any intercurrent events (e.g. whether they refused or discontinued the treatment or whether other protocol violations are revealed).

The per-protocol (PP) population is a subset of the ITT population and is defined as the group of subjects who had no major protocol violations, received a predefined minimum dose of the treatment and underwent the examinations required for the assessment of the endpoints at relevant, predefined times i.e. representing a hypothetical population without intercurrent events and adhering to the protocol. The analysis of the PP group will be performed for the purpose of a sensitivity analysis.

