14.2.5 Methods of Analysis

Statistical analysis will be performed at the Institute of Medical Biometry, Informatics and Epidemiology (IMBIE) at the University of Bonn Medical Center.

To estimate the rates of DGE grades within the defined populations during a 21 days period after surgery after 7 days treatment either with a nicotine or with placebo patch.

These rates will be given together with their respective confidence intervals by treatment group. A comparison of the treatment groups will be performed by means of a proportional odds model (accounting for the stratification factors). The main outcome of this analysis will be an estimate of the odds ratio according to the explorative character of the trial.

Additional sensitivity analyses will be performed to assess the robustness of the results: a dichotomized version of the DGE score will be investigated by means of a logistic regression model.

In both models, the influence of additional covariates like sex, age, or other comorbidities will be investigated (for the purpose of the planning of later phase trials).

Two analysis populations will be defined: intent-to-treat (ITT) and per-protocol (PP). The former includes all randomized patients whereas patients with relevant protocol deviations will be excluded from the latter. The main analysis will be performed within the ITT population.

Safety parameters and secondary endpoints will be summarized by means of descriptive statistics or by absolute and relative frequencies according to the type of the variables by treatment.

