14.2.7 Protocol Violations

Protocol violations are major deviations from the procedures outlined in this document including but not limited to:

- missed evaluations
- incorrect timing of evaluations
- relevant non-compliance with investigational medicinal product, if applicable
- the intake of medications not allowed
- smoking during the IMP treatment phase
- any non-adherence to the protocol that would have an impact to the subject's rights, safety or welfare and or reliability and robustness of study data

After a subject has been enrolled, it is the investigator's responsibility to make a reasonable effort to correct any protocol violations and to continue the subject's participation in the trial, if possible.

Protocol violations do not constitute a justification for withdrawal of a subject from the trial themselves.

Protocol violations will be reported to the sponsor/sponsor delegated person during the course of the trial in the monitoring reports and the clinical study report.

All protocol violations will be listed and the impact on the evaluation of the subjects concerned will be discussed prior to statistical analysis.

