16.2.2 Termination by the Investigator

Subjects may also be withdrawn at any time at the discretion of the investigator for safety, behavioral, or administrative reasons, e.g.:

- Occurrence of intolerable adverse events and which would constitute an unacceptable high risk for the subject
- Lack of efficacy
- Medically indicated e.g. because it is found that inclusion/ exclusion criteria were violated
- Continuation is unacceptable because risks outweigh the benefits
- Pregnancy
- Lack of compliance of the subject (e.g. taking prohibited medication)
- Significant protocol violations
- Logistical reasons (e.g. subject changes his/her doctor or hospital or moves to another location)

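### Sections 11.1.4 and 16.2.2 let randomised patients be taken out for violations that Section 14.2.7 says do not justify withdrawal, and Section 10.14.1 does not confine smoking exclusions to the per-protocol set

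*Protocol*

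**What the plan says.** **Analysis population.** Section 14.2.4 analyses subjects in their randomised arm "irrespective of the occurrence of any intercurrent events", and its examples include discontinued treatment and protocol violations. Section 14.2.5 adds: "The main analysis will be performed within the ITT population". It confines exclusion for relevant deviations to the PP set.

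**Violations.** Section 14.2.7 lists disallowed medication, relevant non-compliance and smoking during treatment as violations. It asks the investigator to correct them and keep the subject in the trial where possible, and states: "Protocol violations do not constitute a justification for withdrawal of a subject from the trial themselves".

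**Provisions that pull the other way.**
- Section 10.14.1, on smoking: a data review meeting discusses "whether the subject will be excluded from the analysis or not". No population and no criterion are named.
- Section 11.1.4, on a listed drug given after inclusion: depending on its duration, "the respective patient should to be excluded from the study", as decided by the investigator with the sponsor.
- Section 16.2.2 gives lack of compliance (with prohibited medication as the example), "Significant protocol violations" and "Lack of efficacy" as grounds for withdrawal at the investigator's discretion.

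**Safeguards.** Section 14.2.8 analyses post-randomisation drop-outs with all available data. Section 16.2.3 asks for a complete final examination and every effort to document the outcome.

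**The concern.** The same event carries two instructions. A patient given a prohibited drug is to be kept in the trial under Section 14.2.7, but may be taken out under Sections 11.1.4 and 16.2.2. Sites can follow either text, and may do so differently.

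Lack of efficacy raises a separate problem. The patch is given for 7 days to prevent DGE, and the endpoint is the DGE grade over 21 days. Withdrawing a patient because the patch seems not to work therefore depends on the primary outcome itself, and it can stop the grading that the ITT analysis needs.

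Under Section 10.14.1, smoking after randomisation may differ by arm, because abstaining smokers on placebo receive no nicotine. If such patients left the main analysis, the odds ratio would no longer compare the groups as randomised. A later analysis plan can define the PP set, but it cannot recover days on which DGE was never graded.

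**Working it through.** **1. The passages side by side**

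| Event | Keep in trial and analysis | Take out |
|---|---|---|
| Prohibited drug | 14.2.7, 14.2.4 | 11.1.4; 16.2.2 (lack of compliance) |
| Other significant violation | 14.2.7, 14.2.4 | 16.2.2 |
| Smoking, Days 1–7 | 14.2.7, 14.2.4, 14.2.5 | 10.14.1, population not named |
| Lack of efficacy | 14.2.4 (ITT principle) | 16.2.2 |

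The first two rows are direct conflicts over withdrawal. The third is an ambiguity. The fourth does not conflict with 14.2.7, because lack of efficacy is not a violation; it conflicts with the purpose of the ITT analysis.

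**2. What early withdrawal can hide (Section 11.1.6, Table 1)**

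Tube requirement on postoperative days 8–14, or reinsertion after day 7, is a grade B criterion. Intolerance of solid food counts at day 14 for B and day 21 for C. Tube requirement or reinsertion after day 14 counts for C. A patient who leaves on Day 8 with a tube in place can already meet a grade B criterion. The day-14 and day-21 criteria have not yet arisen and are lost unless grading continues.

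**3. The plan's own precision figure (Section 14.2.3)**

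Inputs: N = 220, 1:1 allocation, grade rates 0.5, 0.25, 0.15, 0.1.
- 1 − Σp³ = 1 − (0.125 + 0.015625 + 0.003375 + 0.001) = 0.855
- Var(log OR) = 12 / (220 × 0.855)
- 90% half-width = 1.645 × √[12 / (220 × 0.855)] = 0.415, which agrees with the stated value of less than 0.42.
- A half-width of 0.42 needs N = (12 / 0.855) × (1.645 / 0.42)² = 215.3, so 216 patients. At most 24 of 240 can be lost for any reason.

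**4. Illustration for smoking exclusions, assuming no true effect**

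From the document: 88 of 274 patients in the retrospective data smoked, and 88/274 × 240 = 77, or about 38.5 per arm.

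Assumed, with no source in the document:
- 20–40% resume on placebo, or 7.7–15.4 patients;
- 10–20% resume on nicotine, or 3.85–7.7 patients;
- all resumers are removed from the main analysis;
- 70–85% of resumers have no DGE, against 50% overall.

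Each arm starts with 60 patients without DGE and 60 with DGE (30, 18 and 12 in grades A, B and C).
- *Low case (7.7 against 3.85 removed, 70% DGE-free).* Placebo keeps 54.61 without and 57.69 with DGE; nicotine keeps 57.305 and 58.845. The any-DGE odds ratio is (58.845/57.305) / (57.69/54.61) = 0.972. The proportional odds fit to all four grades gives 0.976.
- *High case (15.4 against 7.7 removed, 85% DGE-free).* Placebo keeps 46.91 and 57.69; nicotine keeps 53.455 and 58.845. The any-DGE odds ratio is 0.895. The proportional odds fit gives 0.910.
- *Equal numbers removed per arm, or resumers 50% DGE-free.* The odds ratio is 1.00.

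The largest of these shifts is ln 0.910 = −0.094, and 0.094/0.42 = 0.22 of the planned half-width.

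**The case against.** The strongest case on the other side has four parts.

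- **Section 10.14.1 can be read as meaning PP.** Smoking is a listed violation, and Section 14.2.5 excludes deviations from PP only. Planned unblinding follows database closure (Section 10.13), and violations are discussed before the analysis (Section 14.2.7), so a blind decision is implied. This stands as the most coherent reading, but Section 10.14.1 does not say it.
- **Withdrawal is not removal from ITT.** A reader might infer that withdrawn patients drop out of the main analysis or that data collection ends. Sections 14.2.8 and 16.2.3 do not support that. What remains is narrower: neither section requires DGE grading to Day 21.
- **A reader might infer that a patient withdrawn on Day 8 can never be grade B or C.** Table 1 does not support this for grade B, and the investigator may overrule the algorithm. The loss concerns criteria that arise after withdrawal.
- **The rules are discretionary.** Section 16.2.2 says subjects may be withdrawn, and Section 11.1.4 depends on duration, an individual risk assessment and consultation with the sponsor. Section 14.2.7 says only that violations do not *themselves* justify withdrawal. This softens the conflict without removing it, since Section 16.2.2 names significant violations as a ground in their own right.

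A reader might also take 0.91–0.98 as the expected bias. It is an illustration: the resumption rates and the prognosis of resumers are assumed, and removal from the main analysis is something Sections 14.2.4 and 14.2.5 do not permit.

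**Conclusion.** The inconsistency is real and should be resolved, but it does not overturn the ITT main analysis, which the protocol states clearly.

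- Sections 11.1.4 and 16.2.2 conflict with Section 14.2.7 on prohibited medication, non-compliance and significant violations.
- Lack of efficacy as a ground for withdrawal is tied to the outcome and can cut the 21-day grade short.
- Section 10.14.1 is ambiguous about the population it affects.

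The size of any bias is unknown. The smoking illustration gives an odds ratio of 0.91–0.98 under a null effect if resumption is unequal and resumers have a better prognosis, and 1.00 if either assumption fails. The effect of withdrawals is not quantified, because the document gives no rate for them.

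**What to change.** 1. **Section 10.14.1:** state that smoking during treatment can affect PP membership only, that this is decided blind before database lock, and that the subject stays in the ITT analysis.
2. **Sections 11.1.4 and 16.2.2:** reconcile them with Section 14.2.7 by separating discontinuation of the patch from withdrawal from follow-up. The clinical criteria for stopping the patch stay as they are.
3. **Same sections, with a cross-reference in 16.2.3:** state that patients who stop treatment for these reasons, including lack of efficacy, are still graded for DGE to Day 21 and followed to Day 30 unless they withdraw consent.

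The cost is a protocol wording change. Visits to Day 30 are already in the schedule, so little extra follow-up is needed.

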10.14.2 Rescue Therapy

Not applicable.

11 Trial Procedures

11.1 Methods of Assessment and Procedures

The following section will give an overview and adequate explanations to the examinations and procedures to be performed in this trial and will be determined according to the time schedule given in section 2. The results of these assessments and procedures have to be documented on source documents and transferred to the eCRF.

11.1.1 Informed Consent

Refer to 9.5.3

11.1.2 Demographics

For demographics, the following items will be recorded: age, sex, height, weight, BMI

11.1.3 Medical History

The following items will be recorded for medical history:

- Smoking history (PY in the lifetime)
- active smoker (yes/no)
- weight loss (>10% of body weight in the last six months)

Confidential

EU trial No: 2023-503349-71-00/ TransNiDeG

Attachment 001 to SOP MW-009.001

Version 001

Page 38 of 69

Clinical Trial Protocol version 2.0 of 28-JUN-2023

Effective Date: 18-Mai-2022

- bile duct stent in situ (yes/no), diabetes mellitus (yes/no)
- neoadjuvant chemotherapy administered (yes/no)
- previous abdominal surgery (yes/no)
- updated Charlson Comorbidity Index (0 to 37)
- request for current pregnancy and nursing status (females of childbearing potential only)
- infection and allergies since the last 12 months

11.1.4 Concomitant Medication

The following inhibitors and strong inducers of CYP2A6 are prohibited as concomitant medication during the trial:

- Trancylpromine (e.g. Jatrosom®)
- Desipramin (e.g. Norpramin® Pertofrane®)
- Ketoconazole (e.g. Nizoral®, Terzolin®)
- Valproic acid (e.g. Convulex®, Orfiril®)
- Phenobarbital (e.g. Luminal®)
- Pilocarpine (e.g. Salagen®, Spersacarpin®)
- Clotrimazole (e.g. Canesten®)
- Methoxsalen (e.g. Meladinine®)
- Rifampicin (e.g. Eremfat®, Rifa®)

If the above named agents cannot be discontinued for the trial period, patients cannot be included in the study.

If patients already included into the study have to be treated with the above named drugs due to unforeseen circumstances, an individual estimation of the risk has to be performed by the physician in charge. Depending on the duration of the concomitant treatment, the respective patient should to be excluded from the study. This will be decided by the Investigator in consultation with the Sponsor.

The intake of concomitant medication will be documented in the patient's record and in the e-CRF. However, once concomitant medication use is documented, changes (e.g. in dose or added therapies) may not need to be documented unless they contribute to the follow-up of any safety issue (ICH Guideline E19).

11.1.5 In-/Exclusion Criteria

In-/Exclusion criteria will be checked thoroughly after the Screening Visit. Only eligible subjects will be included into the trial by the investigator.

11.1.6 Grading DGE

The parameters are applied for grading delayed gastric emptying (DGE) according to the International Study Group of Pancreatic Surgery definition [1]:

Depending on these parameters, DGE is graded in four grades: none, grade A, grade B and grade C:

DGE grade	No DGE	Grade A	Grade B	Grade C
NGT requirement	< POD 4	POD 4-7	POD 8-14	> POD 14
NGT reinsertion	≤ POD 3	> POD 3	> POD 7	> POD 14
Unability to tolerate solid food on POD		7	14	21
Vomiting/gastric distension	-	±	+	+
Use of prokinetics	-	±	+	+
Nutritional support (pp enteral or parenteral)	No	Possibly yes	Yes	Yes
Prolongation of hospital stay	No	Possibly yes	Yes	Yes
POPF/intraabdominal abscess	No	No	Possibly yes	Possibly yes
Diagnostic evaluation for DGE (Endoscopy, CT)	No	No	Possibly yes	Yes
Interventional treatment (abscess drain, relap)	No	No	No	Yes
Delay of potential adjuvant therapy	No	No	No	Yes

* NGT according to long-term respiration or vacuum therapy is not considered for DGE grading

Table 1: DGE grading

DGE grading should be done considering the algorithm as above. However, the investigator may overrule this grading according to his own judgement in compliance with the International Study Group of Pancreatic Surgery definition [1].

NGT requirement and the ability of solid food intake will be assessed on every day as indicated in the study schedule. The other parameters as per Table 1 will be assessed only on Visit 1.3, 1.7, 2 and 3.

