Attachment 001 to SOP MW-009.001

Version 001

Page 12 of 69

Clinical Trial Protocol version 2.0 28-JUN-2023

Effective Date: 18-Mai-2022

	
 8. Known history of hypersensitivity to nicotine or a component of the investigational drug 9. Systemic skin diseases (e.g. Lupus erythematoses) 10. Immediately after heart attack 11. Severe cardiac arrhythmia 12. Stroke that occurred shortly before 13. Concomitant medication with inhibitors or strong inducers of CYP2A6 (e.g. Trancylpromine, Desipramin, Ketoconazole, Valproic acid, Pheno-barbital, Pilocarpine, Clotrimazole, Methoxsalen, Rifampicin)
Trial Procedures	
Screening-Visit (Day -28 to Day -1)
 
Visit 1 (Day 1, Surgery)
 
Visit 1.2 – 1.7 (Post-operative Day 2 to Day 7)
 
Visit 2 (Post-operative Day 14)
 
Visit 3 (Post-operative Day 21 or discharge – whatever comes first)
 
Visit 4 (Post-operative Day 30, follow Up)

Trial Specific Measurements	
 • Application of IMP-/Placebo-patch • Assessment of primary and secondary endpoints
Investigational trial sites	
This is a multi-center trial with about six (6) investigational trial sites in Germany.

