Attachment 001 to SOP MW-009.001

Version 001

Page 15 of 69

Clinical Trial Protocol version 2.0 of 28-JUN-2023

Effective Date: 18-Mai-2022

	Screening Visit	Treatment Phase		Follow up Phase		End of Trial
Time points (accepted deviation)	Day -28 to Day -1	Day 1 (Surgery)	Day 2 to Day 7	Day 14 (+/- 1 Day)	Day 21 (+/-1 Day) or Discharge	Day 30 (+/- 2 Days)
Visit No.	0	1	1.2 to 1.7	2	3	4
QLQ-C30						√
PAN26						√

¹ according to the definition of the International Study Group of Pancreatic Surgery. NGT requirement + solid food intake on every visit day indicated, all other parameters only on Visit 1.3, 1.7, 2 and 3.

² especially: surgical site infections, cardiovascular events, mortality

³ Visit 1 only Lymphadenectomy, re-intervention, re-operation, nausea, cardiovascular events. Visit 1.2, 1.3, 1.5-1.7 no assessment. Visit 1.4, 2, 3, 4 only pancreatic fistula, postoperative hemorrhage, intra-abdominal fluid collections, re-laparotomy

⁴ Exclusion Criterion No. 5 can only be answered during surgery

3 Abbreviations

AR	Adverse (Drug) Reaction
AE	Adverse Event
AMG	Arzneimittelgesetz
CA	Competent Authority
CI	Coordinating Investigator
CRA	Clinical Research Associate
CRF	Case Report Form
CRO	Contract Research Organization
CTR	Clinical Trial Regulation
DGE	Delayed Gastric Emptying
EC	Ethics Committee
FPFV	First Patient First Visit
FPI	First Patient In
GCP	Good Clinical Practice
GDPR	General Data Protection Regulation
ICH	International Conference on Harmonization
IMP	Investigational Medicinal Product
ISF	Trial site File
LPLV	Last Patient Last Visit
LPO	Last Patient Out
NGT	Naso-gastric tube
PD	Pancreatoduodenectomy
PI	Principal Investigator
SAR	Serious Adverse Reaction
SAE	Serious Adverse Event
SDP	Sponsor Delegated Person
SUSAR	Suspected Unexpected Serious Adverse Reaction
SZB	Study Center Bonn (Studienzentrum Bonn)
UAR	Unexpected Adverse Reaction

4 Trial Administration structure

Coordinating Investigator and Sponsor Delegated Person	[name] Department of Surgery University Hospital Bonn [name] [contact] Email: [contact]
Sponsor	Medical Faculty of the University of Bonn, represented by the Dean [name]
Coordinating institution	Clinical Study Core Unit, Study Center Bonn (SZB) Institute for clinical chemistry and clinical pharmacology University Hospital Bonn [name]
Participating trial site(s)	6 German sites are planned

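### DGE grades depend on when the naso-gastric tube was out or put back, but the protocol requires no tube dates between visits after Day 7 and no DGE grading after discharge

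*Protocol*

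**What the plan says.** **Grading rule.** Table 1 in Protocol 11.1.6 gives the tube row as windows: before POD 4 is no DGE, POD 4-7 is A, POD 8-14 is B, after POD 14 is C. Reinsertion is graded by whether it falls after POD 3, 7 or 14. The food row ("Unability to tolerate solid food on POD") uses three single days: 7, 14 and 21. The investigator may overrule the resulting grade in line with the cited consensus definition.

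**Data collection.** Section 11.1.6 says "NGT requirement and the ability of solid food intake will be assessed on every day as indicated in the study schedule". Footnote 1 to the Schedule (section 2) shows that this does not mean daily: "NGT requirement + solid food intake on every visit day indicated, all other parameters only on Visit 1.3, 1.7, 2 and 3". Grading DGE is ticked for Days 2-7, Day 14 (±1 day) and Day 21 (±1 day) or discharge. It is not ticked for Day 30.

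**End of observation.** The Synopsis defines the last grading visit as "Visit 3 (Post-operative Day 21 or discharge – whatever comes first". Section 14.2.5 nevertheless estimates the grade rates "during a 21 days period after surgery". Section 14.2.2 lists four DGE secondary endpoints (tube, solid food, vomiting or distension, prokinetics) over the same 21 days.

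**Day count.** The Schedule makes Day 1 the day of surgery. The Synopsis labels the following days "Visit 1.2 – 1.7 (Post-operative Day 2 to Day 7" and the next visit "Visit 2 (Post-operative Day 14".

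**The concern.** The primary endpoint is an ordinal grade. Its upper boundaries turn on the day the tube came out and on whether it went back in, yet the required data are tube status on single days. After Day 7 the next required look is Day 14, and the one after that is Day 21 or discharge. Nothing in 11.1.6 or footnote 1 asks sites to look back over the interval or to enter removal and reinsertion dates.

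Observation also ends at discharge, while the stated period is 21 days. Section 6.1 hopes that the treatment will shorten hospital stay, so the length of observation could differ between arms for a reason linked to treatment. At stake are the grade rates, which the Synopsis names as the primary objective, the four 21-day secondary endpoints and, under some conditions, the odds ratio.

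**Working it through.** **1. Day count against Table 1.** Days 2-21 are 20 days. Tube status is scheduled on Days 2, 3, 4, 5, 6, 7, 14 and 21, which is 8 days. 20 − 8 = 12 days have none: Days 8-13 (6) and 15-20 (6). Taking Day and POD as the same, the grade B window (POD 8-14) contains one visit day in seven, and Days 15-21 contain one in seven.

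**2. Cases the schedule cannot tell apart.**
- A tube out on Day 7 (A) and one out on Day 10 (B) give the same status on Day 14.
- A tube reinserted on Day 16 and out by Day 20 (C) need not appear on Day 21.
- A reinsertion after discharge but before Day 21 meets no DGE visit. Footnote 3 limits Visit 4 to fistula, hemorrhage, fluid collections and re-laparotomy. Section 12.4 ends AE documentation at discharge. The Schedule does tick AEs at Day 30, but nothing there asks for tube or food status.

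**3. Food row.** Its cut-offs are nominal visit days, so food status on Days 8-13 and 15-20 separates no grade. Food is exposed only if the patient leaves before POD 14 or 21, or through the day count.

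**4. Day labels.** On the Synopsis labels, Visits 1.7, 2 and 3 fall on POD 7, 14 and 21 and match Table 1. If POD 1 were instead the day after surgery, they would fall on POD 6, 13 and 20, one day short of each cut-off. Table 1 does not say which count it uses. The ±1 day window also lets Visit 2 fall on Day 15, past the B/C tube boundary if Day equals POD.

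**5. The plan's precision figure (14.2.3).** Inputs: p = (0.5, 0.25, 0.15, 0.1), N = 220, 1:1 allocation, 90% interval. Var(log OR) = 12 / [N(1 − Σp³)].
- Σp³ = 0.125 + 0.015625 + 0.003375 + 0.001 = 0.145
- SE = √[12 / (220 × 0.855)] = 0.2526
- half-width = 1.645 × 0.2526 = 0.4155, which reproduces the stated bound of 0.42.

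**6. Effect of misgrading.** All shares below are assumptions; the documents give none.

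*Grade B recorded as A, same share in both arms.* Planned B is 15%, or 0.15 × 220 = 33 patients. At 25%: 15% × 0.75 = 11.3%. At 50%: 15% × 0.50 = 7.5%. The fitted odds ratio stays at about 0.65 when the true value is 0.65.

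*Share f of B recorded as A and the same share of C as B, equal in both arms.* Patients misgraded = 220 × 0.25 × f.

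| f | Misgraded of 220 | 90% half-width | Fitted OR (true 0.65) |
|---|---|---|---|
| 0.10 | 5.5 | 0.416 | 0.651 |
| 0.25 | 13.75 | 0.417 | 0.652 |
| 0.50 | 27.5 | 0.420 | 0.653 |
| 0.75 | 41.25 | 0.423 | 0.652 |

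*The same shifts, different by arm, with no true effect.* f = 0.50 on nicotine and 0.25 on placebo gives an apparent OR of 0.93; 0.75 and 0.25 gives 0.86.

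**The case against.** The strongest reply is that the information will exist. Most of the gap is probably inpatient time, so ward charts should hold the dates. Several Table 1 items, such as reinsertion and interventional treatment, can hardly be answered without looking back. An investigator who knows of a tube on Day 10 can use the override and grade B, and the eCRF manual, which is not at hand, may ask for dates. This stands in part: it rules out saying that the endpoint goes unobserved. But the protocol names no look-back and no source for the unscheduled days, so practice may differ between sites, and the override does not reach events after discharge. An SAP cannot recover dates that sites were not required to collect.

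Three stronger inferences are tempting and not supported:
- A reader might infer that unscheduled food checks blur the grades in the same way. The single-day food cut-offs rule this out.
- A reader might infer from 11.1.4, where "changes (e.g. in dose or added therapies) may not need to be documented", that prokinetic use is lost. It is a separate Table 1 item asked at Visits 1.3, 1.7, 2 and 3.
- A reader might infer that missed B episodes drop to no DGE and dilute the effect. For 25-50% of B this would move an OR of 0.65 to about 0.67-0.69. But a tube in place continuously to Day 9 is seen on Days 4-7 and grades at least A, so only isolated later reinsertions could fall that far. Even 0.686 is a shift of ln(0.686/0.65) = 0.05, against a planned half-width of 0.42.

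It is also fair that equal misgrading barely touches the odds ratio, which 14.2.5 names as the main outcome of an exploratory trial.

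**Conclusion.** The point holds for the tube and reinsertion criteria and for the period between an early discharge and Day 21. The protocol grades by dates that it does not require to be recorded, and it stops grading before the end of its own 21-day period in patients who leave early. Grade B and C episodes can be under-graded. That this happens systematically cannot be shown, because chart review and the override may rescue some grades.

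The size is unknown. On the assumed 25-50% loss of B to A, the B rate falls from 15% to 11.3-7.5% and the odds ratio is about unchanged. The harm therefore falls first on the grade rates and the 21-day secondary endpoints. The odds ratio is biased mainly if misgrading differs by arm (0.93 or 0.86 under no effect, for the assumed differences). That is possible because observation ends at discharge, but the documents do not show that it will occur. The day-count question is an ambiguity to reconcile, not a demonstrated one-day error. This should be fixed; it does not undermine the design.

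**What to change.** - In 11.1.6 and footnote 1, require dates from the inpatient chart at Visits 1.7, 2 and 3, through Day 21: tube removal, each reinsertion and its removal, and the first day solid food was tolerated.
- At Visit 4, ask about tube reinsertion, loss of solid intake or readmission between discharge and Day 21, and finalise the DGE grade then.
- Separately, reconcile the Schedule's day count (Day 1 is surgery, the next day is labelled Post-operative Day 2) and the ±1 day visit windows with the POD cut-offs in Table 1, and state one count in both places.

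**Cost:** a wording change, some eCRF fields and a little more data entry. No visit is added, since Visit 4 already exists. The drawback is that part of the post-discharge information will rest on patient recall.
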